#### 5.2.2.2 Patients who undergo a stereotactic brain biopsy:

After performing the tumor biopsy, the study neurosurgeon will place a Rickham into brain tissue through the biopsy track.

**Dose level -1 (if a decision is made to dose reduce the NSCs):**  $3.75 \times 10^7$  NSCs in 0.6 ml of 2% HSA/artificial CSF will be manually injected in the operating room over 10 minutes through the Rickham, followed by a 0.3 ml artificial CSF flush.

**Dose level 1:**  $5 \times 10^7$  NSCs in 0.75 ml of 2% HSA/artificial CSF will be manually injected in the operating room over 10 minutes through the Rickham, followed by a 0.3 mL artificial CSF flush.

**Dose level 2:**  $1 \times 10^8$  NSCs will be administered as follows:  $5 \times 10^7$  NSCs in 0.75 mL of 2% HSA/artificial CSF will be manually injected in the operating room over 10 minutes through the Rickham, followed by a 0.3 mL artificial CSF flush. After the patient is out of Recovery and in a hospital room, the remainder of the dose,  $5 \times 10^7$  NSCs in 0.75 ml 2% HSA/artificial CSF,

will be administered via the Rickham followed by a 1 ml flush of artificial CSF. The rate of the infusion will be 0.5 ml/hr, and the total length of time for infusing the NSCs and the flush will be approximately 2 hours.

**Dose level 3**  $1.5 \times 10^8$  NSCs will be administered as follows:  $6.7 \times 10^7$  NSCs in 1 ml of 2% HSA/artificial CSF will be manually injected in the operating room over 10 minutes through the Rickham, followed by a 0.3 ml artificial CSF flush.

After the patient is out of Recovery and in a hospital room, the remainder of the dose,  $8.3 \times 10^7$  NSCs in 1.25 mL of 2% HSA/artificial CSF, will be administered through the Rickham followed by a 1 ml flush of artificial CSF. The rate of the infusion will be 0.5 ml/hr, and the total length of time for infusing the NSCs and the flush will be approximately 3 hours.

**Dose level 4:** As per dose level 3.

A non-contrast CT scan of the brain will be performed after surgery. Patients will have a brain MRI performed on post-operative day 2.

#### 5.2.1.3 Perioperative prophylaxis

Prophylactic anti-convulsants will be administered to study patients. Those who have never had a seizure will continue taking anti-seizure medication for at least 4 weeks after craniotomy or biopsy.

Perioperative antibiotics, corticosteroids, and deep vein thrombosis prophylaxis will be used according to the standard of care for the surgical procedure.

#### 5.2.3 Cycle 1 Day 2: MRI

All patients will undergo an MRI on day 2 (the day after surgery). This MRI will serve as the baseline MRI.

#### 5.2.4 Cycle 1 Days 4-10: Administration of 5-FC (and leucovorin for dose level 4 patients)

If the patient has recovered well from any immediate post-operative effects, is tolerating oral intake, and requiring less than 16 mg/day of dexamethasone by day 4, then s/he will take oral 5-FC, 37.5 mg/kg every 6 hours (dose level 4 and expansion cohort patients will also take oral leucovorin, 25 mg every 6 hours) on days 4-10.

The patient will be discharged from the hospital when medically ready and may proceed with or finish taking the 7-day course of 5-FC (and leucovorin if on dose level 4) as an outpatient.

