#### **4.4 Dose Level Assignment**

Please see section 5.7.

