#### 5.2.5 Cycle 1 Day 15: Intracerebral administration of NSCs via the Rickham

Please see section 6.3 for criteria that a patient must meet in order to proceed with a second dose of NSCs on day 15.

The NSCs will be administered in the outpatient setting through the Rickham at a rate of 0.5 ml/hr.

The maximum concentration of NSCs is  $6.7 \times 10^7$ /ml (or  $1 \times 10^8/1.5$  ml).

**Dose level -1 (if a decision is made to dose reduce the NSCs):**  $3.75 \times 10^7$  NSCs will be suspended in 0.6 ml of 2% HSA/artificial CSF, and the infusion tubing will be primed with the NSC suspension before beginning infusion of the NSCs. A 1 ml artificial CSF flush will follow

the infusion of NSCs. The total length of time for infusing the NSCs and flush will be a little over 3 hours.

**Dose level 1:**  $5 \times 10^7$  NSCs will be suspended in 0.75 ml of 2% HSA/artificial CSF, and the infusion tubing will be primed with the NSC suspension before beginning infusion of the NSCs. A 1 ml artificial CSF flush will follow the infusion of NSCs. The total length of time for infusing the NSCs and flush will be approximately 2 hours.

**Dose level 2:**  $1 \times 10^8$  NSCs will be suspended in 1.5 ml of 2% HSA/artificial CSF, and the infusion tubing will be primed with the NSC suspension before beginning infusion of the NSCs. A 1 ml artificial CSF flush will follow the infusion of NSCs. The total length of time for infusing the NSCs and flush will be approximately 3 ½ hours.

**Dose level 3:**  $1.5 \times 10^8$  NSCs will be suspended in 2.25 ml of 2% HSA/artificial CSF, and the infusion tubing will be primed with the NSC suspension before beginning infusion of the NSCs. A 1 ml artificial CSF flush will follow the infusion of NSCs. The total length of time for infusing the NSCs and flush will be approximately 5 hours.

**Dose level 4:** As per dose level 3.

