#### **5.2.7 Cycle 1 Days 18-24: Administration of 5-FC (and leucovorin for dose level 4 patients)**

Dosing of 5-FC (and possibly leucovorin) as per the dose level the patient is on (see the dose escalation schema table in section 5.1)

Prochlorperazine 10 mg p.o. every 6 hours (or a similar strength anti-emetic) will be used as needed.

Study patients will be evaluated by their treating physicians in clinic on day 22 (as per section 10.0 Study Calendar).

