#### **5.3 Repeat Cycles of Study Treatment**

A treatment cycle is defined as 28 days.

Repeat cycles of study treatment will be administered as long as there is no evidence of progressive disease, and treatment with the NSCs and 5-FC (and leucovorin, as indicated) is well tolerated.

Please see section 6.3 for criteria that the patient must meet in order to or proceed with study treatment on days 1 and 15 of a cycle, as well as instructions for dose modifications if needed with repeat doses of study treatment.

There will be no intra-patient dose escalation of NSCs, 5-FC, or leucovorin.

The NSCs will be administered in the outpatient setting via a Rickham on days 1 and 15 of a cycle, as per section 5.2.4.

5-FC (and leucovorin, as indicated) will be taken by the patient on days 4-10 and days 18-24 as per the dose level the patient is in (see the dose escalation schema table in section 5.1).

Prochlorperazine 10 mg p.o every 6 hours (or a similar strength anti-emetic) will be used as needed.

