## 5.6 Study Design

The study will implement a standard 3+3 design. The goal will be to determine the maximum tolerated dose (MTD), which is defined as the highest dose level tested in which fewer than 33% of patients experienced a DLT attributable to the treatment regimen of NSCs with 5-FC and leucovorin, when at least 6 patients were treated at that dose and are evaluable for toxicity. If the MTD has not been reached with 1.5 x 108 NSCs, 37.5 mg/kg q6h 5-FC and 25 mg q6h leucovorin (dose level 3 plus leucovorin), then that dose will be termed the maximum feasible dose (MFD).

- 5.6.1** Phase I cohorts will be of 3 or 6 participants, as indicated by the dose-escalation criteria.
- 5.6.2** The dose schedule is provided in the table in section 5.7. The first cohort of patients will start at dose level 1.
- 5.6.3** Dose escalation will proceed through the identified doses without skipping any dose levels.
- 5.6.4** *Enrollment of the first 3 patients to dose levels 1-3 will be staggered* by requiring that each of the first 3 patients be separately observed for 4 weeks (or until the DLT assessment period has ended) before the next patient can start treatment on that dose level.
- 5.6.5**
- 5.6.6** Dose escalation rules:
  - 5.6.6.1 If 0/3 study participants experiences a DLT, the next cohort of 3 study patients will be treated at the next higher dose level.
  - 5.6.6.2 If 1/3 study participants experiences a DLT, the cohort will be expanded by another 3 study participants who will be treated at the same dose level for a total of 6 study participants.
  - 5.6.6.3 If 1/6 participants experiences a DLT, the next cohort of 3 study participants will be treated at the next higher dose level.
  - 5.6.6.4 If 2 or more participants of either a 3 participant or 6 participant cohort encounter a DLT, then the MTD has been exceeded. If applicable, three (more) participants will be enrolled at the next lower dose level.
  - 5.6.6.5 At least 6 patients will be treated at the MTD (or MFD, if the MTD is not reached).

For a patient to be counted for dose escalation, s/he must receive at least 80% (+/- 5%) of the assigned NSCs on days 1 and 15 and 80% (+/- 5%) of the 5-FC (and leucovorin, as indicated) on days 4-10 and 18-24 during cycle 1 and be followed up to and including cycle 2 day 1 safety assessments or have experienced a DLT.

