## 5.7 Dose Escalation Schema

Dose Level	Neural Stem Cells (i.c. on days 1 & 15)	5-FC (mg/kg q 6h p.o. on days 4-10 & 18-24)	Leucovorin (mg q 6h p.o. on days 4-10 & 18-24)	Initial Enrollment	If 1 DLT, additional enrollment
------------	---	---	--	--------------------	---------------------------------

-1 a	$3.75 \times 10^7$	28	---	3	3
1	$5 \times 10^7$	37.5	---	3	3
2	$1 \times 10^8$	37.5	---	3	3
3	$1.5 \times 10^8$	37.5	---	3	3
4 b,c	Highest tolerated dose combination of 5-FC and NSCs		25	3	3

aIf a DLT is observed in 2 or more patients at dose level 1, then a de-escalation dose, **dose level -1** will be tested. With dose level -1, the doses of NSCs and 5-FC will both be reduced by 25%; however, if the DLT can clearly be attributed only to 5-FC, then only the dose of 5-FC will be reduced by 25% (likewise for the NSCs if the DLT is clearly attributable to only the NSCs) for dose level -1.

bIf the addition of leucovorin to the highest tolerated dose combination of 5-FC and NSC requires a dose de-escalation, then leucovorin will be discontinued and the MTD/MFD will be the highest tolerated dose combination of 5-FC and NSCs without leucovorin. A total of 6 patients will be treated at the maximum tolerated dose (MTD), or if the MTD is not reached, at the maximum feasible dose (MFD).

cPatients on dose level 4 will undergo intracerebral microdialysis to measure NSC-mediated conversion of 5-FC to 5-FU.

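### Section 5.2.4 fixes the first 5-FC course at 37.5 mg/kg for everyone, contradicting the 28 mg/kg that the dose table sets for dose level -1

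*Combined protocol and SAP*

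**What the plan says.** Section 5.2.4 governs the first 5-FC course. Once the patient has recovered from surgery, tolerates oral intake and meets the dexamethasone limit, "then s/he will take oral 5-FC, 37.5 mg/kg every 6 hours". The only dose-level distinction there concerns leucovorin. The Days 4-10 bullets in the Experimental Design Schema and in section 5.1 give the same flat 37.5 mg/kg.

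The dose table appears four times (front schema, synopsis, sections 5.1 and 5.7). Each copy lists dose level -1 at 3.75 x 10^7 NSCs and 28 mg/kg 5-FC every 6 hours. Footnote a opens that level after DLTs in two or more level 1 patients, and by default "the doses of NSCs and 5-FC will both be reduced by 25" per cent. If the DLT is clearly due to one agent alone, only that agent is reduced.

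Other sections follow the table:

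- Section 4.4, on dose assignment: "Please see section 5.7".
- Section 5.6.2: "The dose schedule is provided in the table in section 5.7".
- Section 5.2.7, on days 18-24 of cycle 1: "Dosing of 5-FC (and possibly leucovorin) as per the dose level the patient is on".
- Section 5.3, on later cycles: 5-FC "will be taken by the patient on days 4-10 and days 18-24 as per the dose level the patient is in".
- Sections 5.2.2.1, 5.2.2.2 and 5.2.5, on the NSCs, each carry a separate line beginning "Dose level -1 (if a decision is made to dose reduce the NSCs".

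**The concern.** The first 5-FC course is the only part of the treatment plan with no provision for dose level -1. The NSC sections have one, and the later 5-FC courses defer to the assigned level. This looks like an oversight in a dosing instruction, not a design choice.

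Level -1 exists to lower the dose after level 1 has proved too toxic. If 5.2.4 were applied as printed with 5-FC reduced, those patients would start on the unreduced 5-FC dose, then drop to the reduced dose on days 18-24 under 5.2.7.

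The evaluability rule in section 5.6 would not exclude them. It requires at least "80% (+/- 5%) of the 5-FC (and leucovorin, as indicated) on days 4-10 and 18-24" and sets no upper limit, so an overdosed patient still counts toward the level -1 decision. The extra drug would tend to add DLTs at level -1, not hide them. What is at stake is therefore mainly the exposure of that cohort, and secondly a DLT count that does not describe the nominal level -1 dose.

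**Working it through.** **Inputs.** 5-FC 37.5 mg/kg every 6 hours (5.2.4); 28 mg/kg every 6 hours at level -1 (5.7 table); 25% reduction (footnote a); 7-day courses on days 4-10 and 18-24; rounding to the nearest 250 mg (8.2.5); second course dosed by level (5.2.7).

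**Reproducing the table.** 37.5 x (1 - 0.25) = 28.125, printed as 28. For the NSCs, 5 x 10^7 x 0.75 = 3.75 x 10^7, as printed. The table and footnote a agree with each other, so the outlier is 5.2.4.

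**The branches of footnote a.**

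| Agent reduced | 5-FC under 5.7 (mg/kg) | 5-FC under 5.2.4 (mg/kg) | Conflict |
|---|---|---|---|
| Both (default) | 28 | 37.5 | Yes |
| 5-FC only | 28 | 37.5 | Yes |
| NSCs only | 37.5 | 37.5 | No |

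**Size without rounding.**

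- Per dose: 37.5 / 28 = 1.339, or 34% more.
- Doses per course: 4 per day x 7 days = 28.
- First course: 37.5 x 28 = 1050 mg/kg against 28 x 28 = 784 mg/kg, a difference of 266 mg/kg.
- Cycle 1 total, second course at the assigned level: (37.5 + 28) / (2 x 28) = 1.170, or 117% of assigned.

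**Size with 250 mg rounding.** The weights are assumptions.

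| Weight (kg) | 5.2.4 dose (mg) | Level -1 dose (mg) | Extra in course 1 | Cycle 1 total / assigned |
|---|---|---|---|---|
| 60 | 2250 | 1750 | 500 x 28 = 14 g | 4000 / 3500 = 114% |
| 80 | 3000 | 2250 | 750 x 28 = 21 g | 5250 / 4500 = 117% |
| 100 | 3750 | 2750 | 1000 x 28 = 28 g | 6500 / 5500 = 118% |

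The last column uses per-dose amounts, first-course dose plus second-course dose over twice the level -1 dose. Every case clears the 80% minimum in 5.6.

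**How often level -1 might open.** The documents give no expected DLT rate, so this is illustrative only. For an assumed true rate p at level 1, the chance of exceeding it on the first pass is 1 - (1-p)^3 - 3p(1-p)^2 x (1-p)^3. That is 9% at p = 0.10, 40% at 0.25 and 57% at 0.33. It leaves out a return to level 1 after level 2 fails, and it includes the NSC-only branch, where there is no conflict. The documents give no basis for splitting DLTs by causal agent, so no probability of the conflict itself is claimed.

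**A related slip.** The Days 18-24 bullets, in the same two places, print 37.5 mg without the per-kilogram unit. Section 5.2.7 gives the right rule for those days. This is an evident typing error and adds no weight to the main point, but the same edit removes it.

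**The case against.** The strongest reply is that nobody would be misled. Sections 4.4 and 5.6.2 make the 5.7 table the source of the dose, 5.2.7 and 5.3 dose by level, and each set of bullets sits beneath a table showing 28 mg/kg. Level -1 cannot open without a judgement under footnote a on which agent to cut, so following 5.2.4 would mean reversing a decision just made. The tracking log in section 7.2 records doses given. Under section 12.2 the drug service needs the principal investigator's approval to release agent that would cause a deviation, it turns to the investigator when the text is ambiguous, and deviations reach the DSMC within five days. Level 1 also repeats the pilot study's top doses, reported as well tolerated, so level -1 may never open.

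Most of this stands. The intended dose is clear and a silent error is unlikely. The pilot evidence makes level -1 less likely but does not rule it out, because the pilot gave a single course.

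Two things remain. Section 5.2.4 is operative treatment text, not a summary, and nothing in it makes its figure subject to the table. And a deviation check compares what is dispensed with what the protocol orders: 37.5 mg/kg complies with 5.2.4, so the check need not trigger. Relying on the investigator to settle an ambiguity at the time is weaker than removing it beforehand.

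**Conclusion.** The concern holds. Section 5.2.4 and the Days 4-10 bullets state a wrong 5-FC dose for dose level -1 whenever 5-FC is reduced, which is the default there.

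The scope is narrow: level -1 must open, the DLTs must not be clearly due to the NSCs alone, and only days 4-10 of cycle 1 are affected. Within that scope the excess is 34% per dose and 17% over cycle 1 before rounding, or 14 to 28 g in the first course at assumed weights of 60 to 100 kg. These figures assume that 5.2.4 is followed literally and that 5.2.7 is followed for the second course.

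The likely bias is toward more DLTs at level -1. Sample size, the confidence limits and the analysis plan are unaffected. It should be corrected because it is a contradictory dosing instruction for a cohort that exists to receive less drug.

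**What to change.** In section 5.2.4, and in the Days 4-10 and Days 18-24 bullets of both the Experimental Design Schema and section 5.1, replace the fixed figure with 5-FC at the assigned dose level, citing the table and footnote a in section 5.7. This keeps 37.5 mg/kg where only the NSCs are reduced, gives 28 mg/kg otherwise, and removes the missing per-kilogram unit.

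The cost is wording in five lines: 5.2.4 and four bullets. The background text in section 2.6.1 repeats the flat dose and could be aligned at the same time, though it gives no treatment order. Nothing in the design, sample size or analysis changes.

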#### 5.2.4.1 Anti-emetic medication

If nausea develops, prochlorperazine 10 mg p.o. every 6 hours (or a similar strength anti-emetic) will be used as needed.

#### 5.2.5 Cycle 1 Day 15: Intracerebral administration of NSCs via the Rickham

Please see section 6.3 for criteria that a patient must meet in order to proceed with a second dose of NSCs on day 15.

The NSCs will be administered in the outpatient setting through the Rickham at a rate of 0.5 ml/hr.

The maximum concentration of NSCs is  $6.7 \times 10^7$ /ml (or  $1 \times 10^8/1.5$  ml).

**Dose level -1 (if a decision is made to dose reduce the NSCs):**  $3.75 \times 10^7$  NSCs will be suspended in 0.6 ml of 2% HSA/artificial CSF, and the infusion tubing will be primed with the NSC suspension before beginning infusion of the NSCs. A 1 ml artificial CSF flush will follow

the infusion of NSCs. The total length of time for infusing the NSCs and flush will be a little over 3 hours.

**Dose level 1:**  $5 \times 10^7$  NSCs will be suspended in 0.75 ml of 2% HSA/artificial CSF, and the infusion tubing will be primed with the NSC suspension before beginning infusion of the NSCs. A 1 ml artificial CSF flush will follow the infusion of NSCs. The total length of time for infusing the NSCs and flush will be approximately 2 hours.

**Dose level 2:**  $1 \times 10^8$  NSCs will be suspended in 1.5 ml of 2% HSA/artificial CSF, and the infusion tubing will be primed with the NSC suspension before beginning infusion of the NSCs. A 1 ml artificial CSF flush will follow the infusion of NSCs. The total length of time for infusing the NSCs and flush will be approximately 3 ½ hours.

**Dose level 3:**  $1.5 \times 10^8$  NSCs will be suspended in 2.25 ml of 2% HSA/artificial CSF, and the infusion tubing will be primed with the NSC suspension before beginning infusion of the NSCs. A 1 ml artificial CSF flush will follow the infusion of NSCs. The total length of time for infusing the NSCs and flush will be approximately 5 hours.

**Dose level 4:** As per dose level 3.

#### **5.2.6 Cycle 1 Day 15: Immunologic correlative studies**

While data from the first study of these CD-expressing NSCs showed no evidence of NSC immunogenicity after first exposure, since patients in this study will receive more than 1 dose of NSCs, we will monitor for development of immune responses after repeat exposure to the NSCs by taking samples of blood from study patients prior to the start of study treatment, on day 15 of cycle 1, as well as during subsequent treatment cycles (please see section 5.3.1 for further details) to assess for the development of anti-NSC T-cell and/or antibody responses and to look for peripheral persistence of the NSCs (please see section 9.1 for further details).

Additionally, aliquots of serum will be saved from the blood samples drawn for immunologiccorrelative studies prior to start of study treatment and on day 15 of cycle 1 to serve as a baseline comparison if a patient were to develop signs/symptoms of a possible immune response to the NSCs during a subsequent treatment cycle. These serum samples, along with additional serum samples drawn at the time the patient develops clinical findings suspicious for an immune response, will be analyzed via Luminex cytokine panels (please see sections 6.3.3.2, 9.1.4, and 9.1.5.4).

#### **5.2.7 Cycle 1 Days 18-24: Administration of 5-FC (and leucovorin for dose level 4 patients)**

Dosing of 5-FC (and possibly leucovorin) as per the dose level the patient is on (see the dose escalation schema table in section 5.1)

Prochlorperazine 10 mg p.o. every 6 hours (or a similar strength anti-emetic) will be used as needed.

Study patients will be evaluated by their treating physicians in clinic on day 22 (as per section 10.0 Study Calendar).

#### **5.3 Repeat Cycles of Study Treatment**

A treatment cycle is defined as 28 days.

Repeat cycles of study treatment will be administered as long as there is no evidence of progressive disease, and treatment with the NSCs and 5-FC (and leucovorin, as indicated) is well tolerated.

Please see section 6.3 for criteria that the patient must meet in order to or proceed with study treatment on days 1 and 15 of a cycle, as well as instructions for dose modifications if needed with repeat doses of study treatment.

There will be no intra-patient dose escalation of NSCs, 5-FC, or leucovorin.

The NSCs will be administered in the outpatient setting via a Rickham on days 1 and 15 of a cycle, as per section 5.2.4.

5-FC (and leucovorin, as indicated) will be taken by the patient on days 4-10 and days 18-24 as per the dose level the patient is in (see the dose escalation schema table in section 5.1).

Prochlorperazine 10 mg p.o every 6 hours (or a similar strength anti-emetic) will be used as needed.

### **5.3.1 Immunologic correlative studies**

In addition to the blood samples drawn prior to the start of study treatment and on cycle 1 day 15, **blood samples will be drawn on days 1 and 15 of cycle 2 and then on day 15 of subsequent cycles** for continued assessment of possible development of anti-NSC T cell and/or antibody responses (please see section 9.1 for further details).

A decision to stop study treatment will be based on development of clinical signs/symptoms of an immune response rather than a particular level of anti-NSC T cells or antibodies (please see section 6.3.3 for further details).

### **5.3.2 Assessment of response**

A brain MRI will be performed at the end of even cycles of study treatment (Day 28 (-3 days) of cycle 2, 4, 6 etc.).

